| Anthropometric measures^ | | X | X | X | X |
| Orthostatic Hypotension Assessment [^] | | Х | X | X | Х |
| Quality of Life measures: | | | | | |
| NeuroQol | | X | X | X | X |
| Questionnaires | | X | Х | Х | X |
| Demographics | | X | | | |
| Functional Assessments | | | , . | , . | |
| Berg Balance Scale [^] | | X | X | X | X |
| 8-foot Get Up and Go Test^ | | X | X | X | X |
| Modified Falls Efficacy Scale | | Х | X | Х | Х |
| Aerobic Assessment | | | | | |
| VO2 max | X | | | | X ⁺ |
| | | | | | |
| Dual Energy X-ray Absorptiometry | | | | | |
| Duai Lineigy A-iay Absorptionietry | | X | | | X |

^{*}Randomization to exercise protocol to occur after baseline visit

Data collected for clinical purposes as part of the Adult Bariatric Surgery Program will be reviewed as part of this study and included in the study records.

- **C3.6. Timeline and milestones:** The planned study duration is 5 yr, with 2 yr of subject accrual, 2 yr of subject follow-up, plus 1 yr for analysis and results presentation.
- **C3.7. Statistical analysis:** The four treatment groups (HIIT/no surgery, HIIT/surgery, routine exercise/no surgery, routine exercise/surgery) will be compared with respect to demographic and baseline variables (e.g., age, sex, glycemic status, OGIS, BMI, etc.). If a significant difference is found in any variable, the models described below will be fitted after adjusting for these variables.
- C3.7.1 Analysis of primary outcome: The primary outcome is IENFD at the proximal thigh, measured at baseline, 3, 12, and 24 mo. Exploratory analysis will be performed to assess the need for any transformation

^{*}Only participants randomized to the HIIT will complete a second time

 $^{^{\}mathsf{T}}$ Participants can consent to have skin biopsy added to biorepository

[^]Participants may complete the consent and outcomes virtually prior to the upcoming visit to decrease in-person interaction due to Covid-19. If the outcome cannot be completed successfully it with be completed during the visit.

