on the primary outcome variable. The primary exposure variables are HIIT: yes/no (Aim 1), and bariatric surgery: yes/no (Aim 2). We will adjust for demographic, clinical, and baseline characteristics as covariates in the model. In addition to the main effects of HIIT exercise program and bariatric surgery, we will also examine selected interactions based on *a priori* considerations. In particular, we will focus on the interaction between HIIT and bariatric surgery to assess if the effect of HIIT exercise on IENFD is modified by bariatric surgery. Linear mixed effects regression modeling will be used to determine the relationship between the primary exposure variables and IENFD over time. Longitudinal data analysis approaches such as this offer enhanced statistical power, as subjects are able to serve as their own reference. Furthermore, linear mixed effects regression offers a flexible framework to handle missing data such as due to attrition. Let Y_{it} denote the IENFD of the *i*th patient at the *t*th time point. Then Y_{it} can be modeled using the random intercept model.¹¹⁴ The random intercept model can be viewed as arising from a two-stage model as follows:

Stage 1: subject-specific trajectory: $Y_{it} = \mu_{0i} + \lambda' Z_i + \underline{\theta' X}_{it} + \underline{e}_{it}$

Stage 2: between-subjects: $\mu_{0i} = \beta_{00} + \beta_{0i}$

Combining the two stages, we can write $Y_{it} = \beta_{00} + \beta_{0i} + \theta' X_{it} + e_{it}$

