where β_{00} is the population-averaged intercept, Z_i is the matrix of main effects and interaction corresponding to HIIT exercise and bariatric surgery, \underline{X}_{it} is the matrix of fixed covariates (demographic and baseline characteristics), λ and θ are the vectors of corresponding fixed effects parameters, β_{0i} is the subject-specific random (intercept) effect capturing heterogeneity across subjects due to unmeasured confounders, and en is the random error characterizing variation due to sources like within-subject fluctuations and measurement error. The random effect β_{0i} is assumed to follow a normal distribution with mean zero and variance σ^2_{sub} , and the eit's are assumed to be distributed normally with mean **0** and variance covariance matrix R (non-diagonal). Furthermore, we also assume that θ_{0i} and e_{it} are independent. Maximum likelihood method will be used to estimate the model parameters. We will use Akaike Information Criterion (AIC) and Schwarz Bayesian Information Criterion (BIC) to guide the selection of the covariance structure. Inference for λ (which is of primary interest) will be based on Wald tests. We will use PROC MIXED in SAS to fit the above model. To explore potential non-linear or threshold effect of treatment exposure on IENFD we will use a nonparametric regression model fitted using the framework of generalized additive models (GAM). 115 Given the exploratory nature of the research proposed here, the GAM models will allow us the flexibility to include a smooth functional term instead of restricting to a linear relationship. The smoothing term is fitted by using penalized regression splines or locally smoothed loess curves, with the degree of smoothness chosen in a data-adaptive way, using cross-validation techniques. We will use the gam function in the mgcv package available in the R software to fit these non-parametric regression models. We will perform sensitivity analyses to assess how subjects who withdrew affect conclusions of the analysis. An intent-to-treat analysis set (including subjects who are randomized, treated, and have a baseline IENFD) will be used to assess treatment effects, with multiple imputation methods¹¹⁶ employed to impute outcomes for subjects with missing post-baseline data. Depending on the extent and pattern of missingness, other simpler sensitivity analyses may be used: e.g., subjects completing the study (completers) may be analyzed using a repeated measures analysis of variance model. The model will include the same covariates that are included in the primary analysis.

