considerations. However, there are two assumptions necessary to justify the multicenter trial. The first is that HIIT will cause an increase in IENFD (re-innervation) and the second is that the natural progression of DSP is loss of nerve fibers over time. The primary outcome is an assessment of IENFD at the proximal thigh over 4 time points spanning 24 mo in the four trial arms. To estimate the likely effect sizes of the four interventions, we will rely on previous well-conducted studies, including our ongoing NIH K23 project. For the routine exercise/no surgery group, we estimate that the IENFD will decrease similar to that observed for those with pre-diabetes and DSP. Over 26.7 mo, IENFD at the proximal thigh decreased from 19±5 to 13±4. Given that our population includes patients with normoglycemia, we expect a decline of at least 3 fibers/mm over the 2 yr of our study. For the HIIT/no surgery group, we estimate that the IENFD will increase by 1.4±2.3 fibers/mm based on a study of the effect of exercise by Smith et al.³⁰ They saw this effect after 1 yr, but we will conservatively estimate that the effect will plateau after the initial yr after the intervention. For routine exercise/surgery group, we estimate that the IENFD will increase by 0.2±7.0 based on our preliminary data on patients undergoing diet-induced weight loss for 2 yr. For the HIIT/surgery group, we estimate that the effect will be additive compared to the two separate interventions. With our expected sample size of 30 patients (allowing for ~15% attrition) in each of the four treatment groups, we will have at least 80% power to detect effect sizes between 0.9 and 1.7 as statistically significant based on a two-sided test with alpha=0.05.

- **C3.9. Data collection and management:** Data report forms will be filled out during each visit, verified, and entered into RedCap. Validation reports will be run, and checked for omissions, improbable values, and data consistency. Distributions of continuous measures will be assessed for symmetry and transformations will be applied as needed. Co-investigator [name], Professor of Biostatistics, [name], graduate student, and [name] will have data access for monitoring and verification.

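### Maximum likelihood with Wald tests makes the primary treatment test modestly liberal; REML with Kenward-Roger degrees of freedom would correct it

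*Protocol*

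**What the plan says.** Protocol section C3.7.1 sets out a random intercept model for proximal-thigh IENFD at baseline, 3, 12 and 24 months. The Stage 1 equation enters treatment as λ'Z_i, where Z_i holds the HIIT and surgery main effects and their interaction. It has no time index, so λ is a constant difference between patients.

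On estimation and testing the section is explicit: "Maximum likelihood method will be used to estimate the model parameters", then "Inference for λ (which is of primary interest) will be based on Wald tests", then "We will use PROC MIXED in SAS to fit the above model". It names neither restricted maximum likelihood nor a reference distribution or degrees-of-freedom method.

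On covariates, C3.7.1 says "We will adjust for demographic, clinical, and baseline characteristics as covariates in the model". The opening paragraph of C3.7 adds a data-dependent set: "If a significant difference is found in any variable, the models described below will be fitted after adjusting for these variables". Neither place gives a number.

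The significance level appears only in C3.8, where effects are to be "statistically significant based on a two-sided test with alpha=0.05". The same sentence gives the evaluable number: "With our expected sample size of 30 patients (allowing for ~15% attrition) in each of the four treatment groups". Section C3.1 gives 140 enrolled, 35 per arm.

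**The concern.** Maximum likelihood estimates variance components as if the fixed effects were known. It divides the residual sum of squares by the number of patients, not by that number less the parameters estimated. For a within-patient contrast with many residual degrees of freedom this hardly matters. For a patient-level effect, which λ is as written, every patient-level covariate in the model uses one of only about 120 to 140 units. The standard error is then understated and the Wald statistic is too large.

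At stake is the calibration of the test and confidence interval for HIIT, the randomised comparison of Aim 1, and for surgery and the interaction. Section C6 says these results will decide which interventions go into a phase 3 trial. Section C3.7.2 carries the same modelling approach to the secondary outcomes, so their intervals are affected too.

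**Working it through.** **Inputs from the protocol.** Maximum likelihood, Wald tests and time-constant λ (C3.7.1); two-sided 0.05 and 30 evaluable per group (C3.8); 35 enrolled per arm (C3.1). The sample sizes agree: 35 × 0.85 = 29.75, about 30; 4 × 30 = 120 evaluable; 4 × 35 = 140 enrolled. The power range in C3.8 is not needed here.

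**Assumed.** The number p of patient-level fixed-effect parameters, because the protocol gives none. The lower end is 4: intercept, HIIT, surgery and interaction, with no covariates. The upper end is 20, which means 16 covariate terms. For orientation, the variables that C3.7 lists as examples for baseline comparison (age, sex, glycemic status, OGIS, BMI) would use 1 + 1 + 2 + 1 + 1 = 6 parameters, with glycemic status in three levels. That makes p = 10 if all were fitted.

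**Formula.** With balanced visits and a random intercept, the estimate of λ is a regression on patient means. Maximum likelihood divides the residual sum of squares by N where the unbiased estimate divides by N − p. So:

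- SE(ML) / SE(unbiased) = √((N − p)/N)
- type I error with a normal reference = 2·P(t(N−p) > 1.96·√((N − p)/N))
- type I error with ML and a t reference = 2·P(t(N−p) > t(0.975; N−p)·√((N − p)/N))

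Worked case, N = 120 and p = 12: √(108/120) = 0.949, so the SE is 5.1% too small. The effective critical value is 1.96 × 0.949 = 1.859, and 2·P(t(108) > 1.859) = 6.6%.

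| N | p | SE too small by | ML, normal reference | ML, t(N−p) reference | REML, normal reference |
|---|---|---|---|---|---|
| 120 | 4 | 1.7% | 5.6% | 5.4% | 5.2% |
| 120 | 8 | 3.4% | 6.1% | 5.8% | 5.2% |
| 120 | 10 | 4.3% | 6.3% | 6.0% | 5.3% |
| 120 | 12 | 5.1% | 6.6% | 6.3% | 5.3% |
| 120 | 20 | 8.7% | 7.7% | 7.3% | 5.3% |
| 140 | 4 | 1.4% | 5.5% | 5.3% | 5.2% |
| 140 | 8 | 2.9% | 5.9% | 5.7% | 5.2% |
| 140 | 12 | 4.4% | 6.3% | 6.1% | 5.2% |
| 140 | 20 | 7.4% | 7.2% | 6.9% | 5.2% |

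REML with a t reference on N − p degrees of freedom gives 5.0% in every row. Most of the excess therefore comes from the estimation method, not from the reference distribution.

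**Simulation check.** Random intercept model, four visits, N = 120, intraclass correlation 0.5 (assumed), normal reference, 10,000 replicates per setting, Monte Carlo error about 0.2 points:

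| Contrast | Method | p = 8 | p = 12 | p = 20 |
|---|---|---|---|---|
| Time-constant HIIT effect | ML | 6.1% | 6.3% | 8.0% |
| Time-constant HIIT effect | REML | 5.2% | 5.2% | 5.4% |
| HIIT by month 24 | ML | 5.8% | 5.2% | 5.4% |
| HIIT by month 24 | REML | 5.5% | 4.9% | 5.1% |

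With 140 enrolled, 15% dropout and 8 covariates (4,000 replicates), the time-constant effect gives 6.3% under ML and 5.1% under REML. The month-24 contrast gives 5.2% and 4.9%. So the closed form holds for λ as written, and the gap is about 0.3 points for a treatment-by-visit change.

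**The case against.** Several points on the other side are sound.

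- **Covariates.** A reader might infer that the plan fits many covariates. It names classes and a few examples, not a count. With none, the excess at 120 patients is 0.6 points. The mild end of the range must be shown beside the other.
- **Sample size.** 120 is the expected number after attrition. A mixed model also uses partly followed patients, so the effective number lies between 120 and 140. The protocol gives no basis for a smaller figure.
- **Normal critical values.** A reader might infer these from the mention of Wald tests. The protocol does not state them, and a degrees-of-freedom method may properly be left to the SAP. The table shows that this does not rescue the plan: ML with a t reference still gives 5.4% to 7.3% at 120.
- **Change over time.** Section C describes the evolution of IENFD from baseline to 2 years, and C3.7.1 speaks of patients as their own reference. For a treatment-by-visit contrast the problem nearly disappears. This is the strongest objection. But the written model contains no such term, and the protocol makes λ the object of inference.
- **Purpose.** A reader might take 0.05 as a guaranteed confirmatory error rate. It stands only in the power statement of a phase 2 trial that calls its research exploratory, and Aim 2 is non-randomised, where confounding matters more than a few per cent in a standard error.

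These points limit the size and weight of the finding. None reverses its direction for λ as specified.

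**Conclusion.** The point holds as a minor one. With maximum likelihood and Wald tests for a time-constant patient-level effect, standard errors are about 2% to 9% too small at 120 patients. Actual type I error is about 5.6% to 7.7%, or 5.5% to 7.2% at 140. These figures rest on an assumed 4 to 20 patient-level parameters, a normal reference and balanced data with a random intercept.

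The documents do not support the stronger conclusion that the trial's false-positive rate is known to be 7% or more. That needs about 16 or more patient-level parameters at 120 patients, which the protocol does not state, and it would not apply if treatment were tested as a change from baseline.

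**What to change.** In C3.7.1, replace maximum likelihood and Wald tests with restricted maximum likelihood and Kenward-Roger t and F tests for the treatment effects (PROC MIXED with METHOD=REML and DDFM=KR on the MODEL statement). Keep AIC and BIC for choosing the covariance structure, computed from the REML fits with the fixed effects held the same across the structures compared.

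The cost is two software options and slightly wider intervals. At 120 patients they widen, against ML with a normal reference, by about 3% with 4 parameters (1.981 / 1.927 = 1.028) and about 11% with 20 (1.984 / 1.789 = 1.109). No patients, visits or measurements change.

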those that do not have surgery. We will also stratify by glycemic status to limit confounding. Randomization will be performed using permuted blocks, with a block size known only to the statistician. We will perform longitudinal analyses using linear mixed models to study the evolution of IENFD from baseline to 2 yr (4 measures in total). We will compare the effect of HIIT, bariatric surgery, and the combination of HIIT and surgery on all outcomes.

C1. Aim 1: Examine the efficacy of a HIIT exercise regimen on DSP outcomes (randomized)

C1.1. Introduction: There is an urgent need for a disease modifying therapy for the prevention and treatment of DSP. Currently, physicians only have neuropathic pain medications and glucose control to offer patients with DSP.^{7, 27} However, glucose control alone is not effective at preventing DSP and many patients with diabetes develop DSP despite good glucose control.²⁷ Similarly, no disease modifying interventions exist for the increasing population with pre-diabetes and/or obesity. Thus, it is essential to identify new interventions that can prevent and treat DSP. To date, uncontrolled studies support improvement in the natural history of DSP decline over time after an exercise intervention.²⁸⁻³⁰ The next step is to determine whether a randomized, intensive, exercise intervention improves DSP outcomes compared to routine exercise counseling.

C1.2. Justification & feasibility:

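### The named sensitivity analyses for withdrawal do not relax the primary model's missing-data assumption, so their agreement with it cannot show robustness to informative withdrawal

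*Protocol*

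**What the plan says.** Section C3.7.1 makes a linear mixed model the primary analysis of proximal-thigh IENFD. It gives as one reason that "linear mixed effects regression offers a flexible framework to handle missing data such as due to attrition", and adds: "Maximum likelihood method will be used to estimate the model parameters". The introduction to section C describes the analysis as following "IENFD from baseline to 2 yr (4 measures in total", so baseline is one of the repeated outcomes.

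The same section then states a purpose: "We will perform sensitivity analyses to assess how subjects who withdrew affect conclusions of the analysis". Two methods are named for it:

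- Multiple imputation, in patients who were randomized, treated and have a baseline IENFD, "employed to impute outcomes for subjects with missing post-baseline data".
- Possibly, once the missingness has been seen, simpler analyses, with the example that "subjects completing the study (completers) may be analyzed using a repeated measures analysis of variance model".

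No shift of imputed values, reference-arm imputation, pattern-mixture rule or other departure from missing at random is described. Section C3.8 plans 30 analysable patients per group, "allowing for ~15% attrition", with the same rate in all four groups.

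**The concern.** A sensitivity analysis for withdrawal is informative when it changes the assumption about what the withdrawn patients' values would have been. The primary model assumes that, given the observed history, a withdrawn patient resembles those in the same arm who remain. Neither named method loosens this. The sponsor could find all three estimates in agreement and conclude that withdrawals do not matter, when the agreement was largely built in.

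The question is a practical one here. HIIT asks for three sessions a week for 24 months (C3.2.1), and control is routine counselling (C3.2.2). Section C4 itself allows that the regimen may prove hard for this population. The retention figures cited, 37 of 40 at 6 months (C1.2.3) and 94% (C3.10.2), come from the team's earlier work, which is not described as including HIIT. The HIIT studies described one by one in C1.2.2 last at most about 12 weeks. Reasons for leaving, and so the link between leaving and IENFD, may differ between arms. The result is meant to inform which intervention goes to phase 3 (C6).

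**Working it through.** **1. The plan's attrition figure.** 35 enrolled per group × 0.85 = 29.75, or about 30. Losing 5 of 35 is 14.3%. The plan's figure reproduces.

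**2. Assumptions side by side.**

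| Analysis | Missing-data assumption |
|---|---|
| Primary maximum-likelihood mixed model | Missing at random |
| Multiple imputation, no stated departure | Missing at random (ordinary reading) |
| Completers ANOVA | Generally missing completely at random |

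Because baseline is a repeated outcome, a patient with only a baseline value already contributes to the mixed model. Imputation therefore brings in nobody new.

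**3. Simulation check.** The setting was 70 versus 70 patients, four visits and 1,500 replicates per mechanism, with about 14% missing at Month 24. The changes at Month 24 are the protocol's (+1.4 and -3, section C3.8). The rest is assumed: SD 5, equal correlation 0.6 between visits, baseline mean 18, and loss of the Month 24 value only. Under the last mechanism, the log-odds of dropout in HIIT were -2.3 - 1.2 × the standardised Month 24 value, and control dropout was random (log-odds -1.79). Imputation used 20 data sets and the same variables as the likelihood analysis. The table gives the mean difference in Month 24 change (fibers/mm).

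| Mechanism | Full data | Likelihood | Imputation | Completers |
|---|---|---|---|---|
| Completely at random | 4.39 | 4.39 | 4.39 | 4.38 |
| At random | 4.41 | 4.42 | 4.42 | 4.42 |
| Not at random (poor Month 24 in HIIT) | 4.42 | 4.80 | 4.80 | 4.70 |

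In the last row the errors are 4.80 - 4.42 = 0.38 for likelihood and for imputation, and 4.70 - 4.42 = 0.28 for completers. Imputation differed from likelihood only by Monte Carlo noise (SD 0.06 per trial). All three are off in the same direction and lie close together. The good behaviour of completers in the middle row comes from the equal-correlation structure and is not general.

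**4. Illustration on the plan's own figures.** The no-surgery contrast is 1.4 - (-3) = 4.4. Suppose all 5 of 35 HIIT withdrawals have no informative post-baseline biopsy and follow the control course:

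- As-randomised effect: 4.4 × 30/35 = 3.77.
- Overstatement: 4.4 - 3.77 = 0.63, and 0.63/3.77 = 17%.

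**5. What a delta shift would reveal.** Lowering the values of HIIT withdrawals by delta moves the HIIT mean by delta × 5/35:

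| Delta (assumed) | Shift in HIIT mean |
|---|---|
| -1 | -0.14 |
| -2 | -0.29 |
| -4.4 | -0.63 |
| -8 | -1.14 |

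The -4.4 row is the scenario of step 4. Neither named analysis would report any of this range.

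**The case against.** **It belongs in the SAP.** Imputation models, shifts and tipping-point grids are usual SAP content, and the SAP is not shown. The protocol does not state the imputation assumption, so calling it the same as the primary model's is a reading of silence. The weekly record of completed sessions (C3.2.1, exercise compliance) could serve as an auxiliary variable. This limits the point but does not remove it: the protocol states a purpose and names methods that, read in the ordinary way, do not serve it. If the SAP already has a missing-not-at-random analysis, the sponsor need only confirm it.

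**The completers run is not worthless.** It is an optional example, and a gap between it and the mixed model could reveal that data are not missing completely at random. That stands. It still cannot reveal departure from missing at random.

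**Stopping training is not leaving the study.** A reader might infer that the planned analyses credit every patient who stops HIIT with the gain of those who continue. The protocol does not support this. Nothing in it ends biopsies when sessions stop, and the separate analysis of patients completing more than 80% of supervised sessions (C3.7.3) implies that less compliant patients remain in the main analysis. Their observed values inform both the mixed model and the imputation.

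**The direction is assumed.** A reader might infer that the error must favour HIIT. That requires HIIT withdrawals to lose benefit and control withdrawals to be uninformative. If control patients who do badly leave, the bias runs the other way.

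**The size is near worst case.** The 4.4 is for the no-surgery stratum. C3.8 calls the combined effect additive without saying how. If changes add, HIIT/surgery is 1.4 + 0.2 = 1.6 against 0.2. The effect in that stratum is then 1.4, the two-stratum average is (4.4 + 1.4)/2 = 2.9, and the overstatement is 2.9 × 5/35 = 0.41. The model as written also has no treatment-by-time term, so it does not clearly estimate a Month 24 contrast. Both limits stand, and the figure is an illustration only.

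**Conclusion.** The point holds in a limited form. The protocol promises analyses to show how withdrawals affect the conclusions, and the methods it names rest on the primary model's missing-at-random assumption or a stronger one. Their agreement cannot show robustness to withdrawal that depends on unobserved IENFD. This conclusion assumes that multiple imputation means standard imputation, as no departure is stated.

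At the planned attrition the possible bias is modest. It is up to about 0.6 fibers/mm on 4.4 in the no-surgery Month 24 illustration, and about 0.3 to 0.4 in the simulation, where dropout on poor outcome was built into HIIT only. It shrinks if withdrawals leave later biopsies or keep some benefit, and it would weigh more if the true effect were smaller than planned.

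A reader might go further and take 17% as the expected error, or assume 30% HIIT attrition, which gives 4.4 × 0.70 = 3.08 and an overstatement of 43%. The protocol gives no basis for 30%, and the 17% rests on near-worst-case assumptions. Nor does the protocol state a numerical threshold for proceeding to phase 3, so nothing shows that a decision would change.

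**What to change.** Before data lock, prespecify at least one missing-not-at-random sensitivity analysis of the primary outcome. A delta-adjusted tipping-point analysis would do: lower the imputed HIIT values in steps until the conclusion changes, and report whether the shift needed is plausible. The step size and range are the sponsor's choice; a shift of 4.4 corresponds to the full control course at the planning values. Imputation of HIIT withdrawals from the routine-counselling arm of the same surgery stratum is a useful optional addition.

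Run this analysis whatever extent or pattern of missingness is seen. Keep standard multiple imputation as the link to the primary model, and treat any completers analysis as supplementary. Continue to use IENFD observed after HIIT sessions stop, so that only values that are truly missing are imputed.

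The cost is some wording and a few extra imputation runs, with no new data and no change to the primary model. The downside is a sensitivity estimate that may be less favourable to HIIT.
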